## **8.2 Day (-1) to day 3 (72 hr after dosing)**

Subjects will become in residence on day -1 and end this period of residency 72 hrs after implantation of BIOPIN 6 or placebo.

On day (-1), the following will occur: medical history update, Physical examination update, concomitant medication update, suicidality repeat, depression repeat, naloxone challenge repeat, , urine drugs repeat, pregnancy urine repeat. EKG repeat. Inclusion/exclusion criteria will be reverified.

On day 1 (0 hr—defined as the beginning of implantation), implantation of BIOPIN 6 or placebo will occur via [Appendix A](#). The measures used to prevent complications of implantation are given at the end of Appendix A.

**In addition to the implant parameters required by Appendix A**, the following assessments will be performed after implantation:

- distance (cm) to the incision of the closest palpable edge of the implant,
- photo of the implant site [outline each palpable implant with a blue marker on subject's skin, metric ruler in photo]

Between 0 hr and 72 hr, vital signs, adverse events, and clinical chemistries and hematology will be evaluated (per study timetable). Blood for PK will be taken Predose and at hours 1, 3, 6, 12, 24, 48 and 72. Acceptable time windows will be +/- 1 hr up to 24 hrs and +/-3 hrs for the 48 and 72 hr draws.

## **8.3 Weeks 1-to-11 after dosing**

Subjects will return for to clinic for a non-residential visit on day 10 and at the end of each week. The following will be assessed weekly: adverse events, concomitant medications. Blood will be drawn for PK on days 7 and 10 and then weekly. Vital signs will be assessed on Days 7 and 10, and on Weeks 2, 3, 4, 5, 6, 7, 8, 9, 10, 11 The following will be assessed at weeks 4 and 8: physical examination, urine drugs, suicidality, depression, clinical chemistries, hematology, EKG, implant assessment (distance from incision, photo of site) as per after-implantation. For these non-residential visits, acceptable time windows will be the target day +/- 3 days.

**The implant parameters required by Appendix A** will be assessed at each residential and non-residential visit, or if the subject brings it to the attention of the study team. The measures used to prevent complications if they occur are given at the end of Appendix A.

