## 2.2 Protocol Timetable

Study Phase	Screening (days -28 to -2)	Day -1	Day 1 to Week 11 	Week 12 (and week 14) 
Informed consent	X			
Demographic data 	X			
Medical history	X	X (update if needed)		
Physical exam 	X	X (update if needed)	Week 4 and 8	X
Weight/height	X			
Urine drugs of abuse screen 	X	X	Week 4 and 8	X
Alcohol breath test	X			
Naloxone challenge test	X	X		
Concomitant medications	X	X	Weekly	X
Serology 	X			
Birth Control Methods/Pregnancy Test 	X	X		
C-SSRS for suicidality	X	X	Weeks 4 and 8	X
HAM-D for depression	X	X	Weeks 2,4,6,8,10	X
Inclusion/exclusion criteria	X	X		
Randomization 		X		
Residential visits		Check in on day (-1)	Check out on Day 4 (72 hours postdose)	Week 12
Non-residential visits	X		Days 7 and 10, and Weeks 2, 3, 4, 5, 6, 7, 8, 9, 10, 11	Week 12 (week 14)
Study drug (Biopin or placebo) administration by implantation			Day 1 (0 h): Insert BIOPIN implant	Remove BIOPIN implant (and week 14) 
Implant Tissue Assessment			At each residential and non-residential visit	Gross and microscopic descriptions and photos of each tissue capsule.

 Age, gender, and race/ethnicity

 Abbreviated (see Protocol Section 8)

 Amphetamines, barbiturates, benzodiazepines, cocaine, opiates, cannabinoids, phencyclidine, propoxyphene, methadone.

 Hepatitis B surface antigen, hepatitis C antibody, human immunodeficiency (HIV-1 and HIV-2) antibodies and p24 antigen, covid antigen

 Serum HCG test at screening; urine HCG test at day (-1). For postmenopausal females, a follicle stimulating hormone test will be performed during screening.

 Each dose cohort of 8 subjects randomized 6 active vs 2 placebo

Study Phase	Screening (days -28 to -2)	Day -1	Day 1 to Week 11 	Week 12 (and week 14) 
Safety and tolerability:				
Adverse event recording	X		Predose, 8, 24, 48 and 72 hours postdose. Then weekly	X
Vital signs 	X		Predose, 8, 24, 48 and 72 hours postdose. Days 7 and 10. Weeks 2, 3, 4, 5, 6, 7, 8, 9, 10, 11	X (pre and post explant)
12-lead ECG	X	X	Week 4 and 8	X (pre and post explant)
Clinical chemistries 	X		72 hours post dose; then weeks 4 and 8	X
Hematology 	X		72 hours post dose; then weeks 4 and 8	X
Coagulation 	X			

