## **8.4 Week 12 and 14: study end**

Subjects will return for a residential visit on week 12 after dosing. Prior to removal, the implant **parameters required by Appendix A** will be assessed (distance from incision, photo of site) as

per after-implantation. At that time, the implant will be removed (Appendix B) and be subject to Gross and microscopic descriptions and photos of each tissue capsule. Blood will be taken for PK pre-explant and 1, 3, 6, 12, 24, 48, 72, 96 hrs after explant. Sampling up to 24 hrs will be as residents; sampling at 48, 72, and 96 hrs (+/- 4 hrs) will be as non-residents. Repeat assessment will be made of adverse effects, vital signs, clinical chemistry, hematology, EKG, concomitant medications, urine drugs, suicidality, depression.

On week 14, 2 weeks after implant removal, the subjects will return for a non-residential visit for surgical evaluation of the implant removal site.

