Blood sampling (29 samples)			Predose. Hours 1, 3, 6, 12, 24, 48 and 72. Days 7 and 10. Weeks 2, 3, 4, 5, 6, 7, 8, 9, 10, 11	Week 12: pre-explant and 1, 3, 6, 12, 24 hrs after explant (as resident). 48,72, and 96 hrs (non resident).

 Heart rate (sitting), blood pressure (sitting), respiratory rate, oral temperature

 ALT, albumin, alkaline phosphatase, AST, bilirubin (total and direct), calcium, chloride, cholesterol, creatinine, GGT, glucose, phosphate, potassium, sodium, total protein, uric acid, and blood urea nitrogen (BUN).

 Hemoglobin, hematocrit, red blood cell count (RBC), reticulocytes, white blood cell count (WBC), platelets

 Fibrinogen, prothrombin time (PT), and partial thromboplastin time (PTT).

 Subjects return for a non-residential visit on week 14 for surgical evaluation of explantation site

 For non-resident days, window will be target day [Week 2 (Day 14), Week 3 (Day 21), etc.] +/- 3 days

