## **10.6. PK Analysis**

Concentration-time profiles will be presented graphically for each subject and by mean  $\pm$  standard error of the mean (SEM) by Biopin 6 group by nominal time point for naltrexone and 6b-naltrexole. The concentration-time profiles will be evaluated by non-compartmental analysis to determine PK parameters. Actual sample times will be utilized for calculations. Calculations of parameters will be performed with Phoenix WinNonLin 8.4 (Certara, Radnor, PA). The elimination rate constants ( $\lambda_z$ ) will be estimated from the terminal log-linear decline in plasma concentrations and  $t_{1/2}$  calculated as  $\ln(2)/\lambda_z$ . Area under the plasma concentration curves will be determined till the last time of a quantifiable plasma concentration ( $AUC_t$ ) by the log/linear trapezoidal rule and to infinity ( $AUC_\infty$ ) based on the last plasma concentration ( $C_t$ ) and  $\lambda_z$ . The value of  $t_{max}$  will be the observed time of the highest plasma concentration and  $C_{max}$  would be the plasma concentration at that time. Mean, SD, geometric mean, median, minimum and maximum will be presented for each PK parameter.

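### SAP Tables 9 and 10 attach the Day 7, Day 10 and Week 2 samples to the wrong nominal times and omit the predose row; overlapping visit windows leave the same stretch without an assignment rule

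*Protocol*

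**What the plan says.** **Schedule.** Protocol Section 2.2 and Section 9.1 schedule 29 PK draws per subject. For the outpatient phase, Section 8.3 says "Blood will be drawn for PK on days 7 and 10 and then weekly".

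**Windows.**
- Section 8.3, outpatient visits: "For these non-residential visits, acceptable time windows will be the target day +/- 3 days".
- Timetable footnote 12, carried into the SAP and attached to both post-dose columns: "For non-resident days, window will be target day [Week 2 (Day 14), Week 3 (Day 21), etc.] +/- 3 days".
- Section 8.2, in-house draws: "Acceptable time windows will be +/- 1 hr up to 24 hrs and +/-3 hrs for the 48 and 72 hr draws". Time zero is "defined as the beginning of implantation".
- Section 8.4, after explant: "sampling at 48, 72, and 96 hrs (+/- 4 hrs) will be as non-residents".

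**Nominal-time output.** SAP Section 10.6 presents mean profiles "by Biopin 6 group by nominal time point for naltrexone and 6b-naltrexole". Tables 9 and 10 are the matching shells. Both print these three consecutive rows: Day 10 at 1.000, Week 2 at 1.429 and Day 7 at 2.000. Neither has a predose row.

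**Parameters.** Protocol Section 9.1 and SAP Section 10.6 both calculate PK parameters from actual sample times, and collection times are recorded.

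**Status.** SAP Section 3 says the plan was finalized after dose-level 2 data were available and escalation had stopped, so these are the shells to be filled.

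**The concern.** PK is the primary endpoint, and Tables 9 and 10 are its concentration-by-time display. In three rows the visit label and the nominal week disagree. If a program selects data by visit label and plots against the week column, the Day 10, Week 2 and Day 7 means land at weeks 1, 1.43 and 2. If it selects by week and prints the label, the values are in the right place but carry the wrong visit name. Either way the populated rows are wrong.

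The windows affect the same stretch. Two in-window draws can fall on one day, and a single draw can belong to either of two visits. Section 7.6.3 allows at most one missed sample from 24 h through Day 10 and at most two from Week 2 to pre-explant. A lone draw on Days 11–13 fits either visit, so which allowance the missing sample uses is undefined. The SAP definition of the PK set (Section 6) asks only for sufficient data and does not settle this.

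**Working it through.** **1. Reproduce the stated sample count.** From the Section 2.2 timetable: 1 predose + 7 (1 to 72 h) + 2 (Days 7 and 10) + 10 (Weeks 2 to 11) + 9 (pre-explant and 8 post-explant) = 29, as stated. Rows in Table 9, and likewise Table 10: 7 + 3 + 9 (Weeks 3 to 11) + 1 (pre-explant) + 8 = 28. The missing row is predose.

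**2. Check the nominal weeks.** Week = hours/168 = days/7. The seven rows from 1 h to 72 h reproduce (1/168 = 0.006; 72/168 = 0.429). The next three do not:

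| Printed label | Printed week | Label's own week | Sample that belongs at the printed week |
|---|---|---|---|
| Day 10 | 1.000 | 10/7 = 1.429 | Day 7 |
| Week 2 (Day 14) | 1.429 | 14/7 = 2.000 | Day 10 |
| Day 7 | 2.000 | 7/7 = 1.000 | Week 2 |

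The week values ascend correctly; only the labels are permuted, by +3, +4 and −7 days.

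**3. Day-count convention.** With 0 h on Day 1, the timetable reads "Check out on Day 4 (72 hours postdose", so elapsed days = day number − 1. Counted that way, Days 7, 10 and 14 are 6/7 = 0.857, 9/7 = 1.286 and 13/7 = 1.857 weeks. The heading of Section 8.2 instead calls 72 h day 3. The printed set 1.000, 1.429, 2.000 implies day/7. The three labels fail under either convention, but the convention should be stated.

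**4. Size if the labels are followed (illustration; BIOPIN 6 concentrations are not in the documents).**
- *Declining profile.* Take the monthly injection's figures from Section 4.4: 10 ng/mL at day 2 and 2 ng/mL at day 28. Assume exponential decline, k = ln(5)/(672 − 48) per hour. Then C = 7.34, 6.09 and 4.76 ng/mL on Days 7, 10 and 14. The shell would show 6.09, 4.76 and 7.34 at weeks 1, 1.429 and 2, errors of about −17%, −22% and +54%.
- *Rising profile*, C = 10(1 − exp(−t/168)): 6.32, 7.60 and 8.65, giving about +20%, +14% and −27%.
- *Flat profile*: 0%.
- *Parameters from actual times*: no change in any case.

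**5. Windows.**
- Outpatient, ±3 days: Day 7 = Days 4–10; Day 10 = Days 7–13; Week 2 = Days 11–17. The first pair shares Days 7–10 and the second Days 11–13. Week 3 (18–24) does not overlap Week 2.
- 1 h draw, ±1 h: 0–2 h. The lower edge is time zero, the start of the procedure. It meets the 3 h window (2–4 h) only at 2 h, so those two do not truly overlap.
- Post-explant, ±4 h: 44–52, 68–76 and 92–100 h, with no overlap. Footnote 12 sits on the same column and does not except these draws.

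**The case against.** The strongest reply is that nothing here reaches the primary objective, which is the PK parameters. They come from recorded actual times, so neither labels nor windows bias them. That stands. A reader might infer that the primary concentration-time profile is itself wrong; the documents do not support it. Individual data and parameters keep their true times, and only the nominal-time summaries are exposed.

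Next, the tables are empty shells, and SAP Section 12 requires independent programming and comparison with listings, which may catch the swap. That is fair, but the same section checks output for consistency with the plan, and a program that follows the shell passes that check. The predose omission is minor, since SAP Section 10.1 puts all data in listings.

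On the post-explant draws, Section 8.4 gives an hour-based window for exactly those samples, while footnote 12 speaks of target days and its examples are weekly visits. The specific rule naturally governs. A reader might set ±72 h against ±4 h and infer an 18-fold conflict, or a factor of 4 to 2 error for a sample 24 h late. The first applies a day-based footnote to draws with their own window. The second needs a post-removal half-life (12 to 24 h) that the documents do not give. What remains is a missing exception in the footnote.

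Finally, same-day draws need one visit late and the next early, a 1 h draw before placement needs the edge of its window, and narrower windows cannot change samples already collected. All true, so the remedy for existing data has to be an analysis rule.

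**Conclusion.** The label error is established from the documents alone: 3 of 28 rows in each of two tables, under either day-count convention, plus one absent row of 29. If populated as written, the Day 7, Day 10 and Week 2 rows would be misattributed for both analytes. Figure 4 would be affected only if it is programmed from the same label-to-week mapping. How large the misplacement looks depends on the unknown profile: nil if flat, and up to about half the true mean at week 2 in the declining illustration. AUC, Cmax, tmax and half-life are unaffected.

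The window overlap is real but secondary. It leaves visit assignment, and the missed-sample count through Day 10, undefined for draws on shared days. A same-day pair would cost a distinct point between 72 h and Week 2 without distorting the time base of the parameters. The post-explant and 1 h points need only clarification.

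**What to change.** **In the SAP, before the tables are populated:**
1. In Tables 9 and 10, relabel the rows Day 7 = 1.000, Day 10 = 1.429 and Week 2 = 2.000, and use that mapping for Figure 4.
2. State how day numbers convert to elapsed time, given that 0 h is on Day 1.
3. Add the predose row to both tables.
4. Add a rule that assigns each draw to one nominal visit by actual time. One example is the nearest target, with cut points (7 + 10)/2 = 8.5 and (10 + 14)/2 = 12 days. Say which draw is summarized if two fall to one visit, how draws far from nominal enter the nominal-time summaries, and that the Section 7.6.3 missed-sample count uses the same assignment.

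**In the protocol and the SAP timetable:**

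5. State in footnote 12 that the 48, 72 and 96 h post-explant draws follow the ±4 h window of Section 8.4.
6. State that the 1 h draw must follow completion of implant placement.
7. For any further enrolment, set windows that do not overlap. Half-widths must sum to less than 3 days for Day 7 and Day 10, and less than 4 days for Day 10 and Week 2. The documents give no basis for particular widths, so the sponsor should choose them.

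Items 1 to 6 cost wording and a small programming specification. Item 7 costs some scheduling freedom at three outpatient visits and cannot change data already collected.

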## **8.4 Week 12 and 14: study end**

Subjects will return for a residential visit on week 12 after dosing. Prior to removal, the implant **parameters required by Appendix A** will be assessed (distance from incision, photo of site) as

per after-implantation. At that time, the implant will be removed (Appendix B) and be subject to Gross and microscopic descriptions and photos of each tissue capsule. Blood will be taken for PK pre-explant and 1, 3, 6, 12, 24, 48, 72, 96 hrs after explant. Sampling up to 24 hrs will be as residents; sampling at 48, 72, and 96 hrs (+/- 4 hrs) will be as non-residents. Repeat assessment will be made of adverse effects, vital signs, clinical chemistry, hematology, EKG, concomitant medications, urine drugs, suicidality, depression.

On week 14, 2 weeks after implant removal, the subjects will return for a non-residential visit for surgical evaluation of the implant removal site.

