**End of study: week 12 (resident, then non-resident)**

Subjects will return for a residential visit on week 12 after dosing. At that time, the implant will be removed and be subject to gross and microscopic descriptions and photos of each tissue capsule. Repeat assessment will be made of adverse effects, EKG, vital signs, clinical chemistry, hematology, concomitant medications, urine drugs, suicidality/depression. To verify diminution

of naltrexone exposure post-implant-removal, blood will be taken for PK pre-explant; 1, 3, 6, 12, 24 hrs after explant (as resident); and 48, 72, and 96 hours after explant (as non-resident).

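### Section 8.4 and the Synopsis do not match the Timetable on the Week 12 physical exam and the pre- and post-explant vital signs and ECG, and four SAP safety tables have no Week 12 row

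*Protocol*

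**What the plan says.** The Protocol Timetable (Section 2.2) has three relevant Week 12 entries.

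- The physical exam row reads "Physical exam 2 X X (update if needed) Week 4 and 8 X". The last mark falls in the combined Week 12 and Week 14 column. The footnote on that row sends the reader elsewhere for content: "Abbreviated (see Protocol Section 8".
- The vital signs row and the 12-lead ECG row both carry "X (pre and post explant".
- Chemistry and hematology carry a plain mark with no timing relative to explant.

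The SAP timetable (SAP Section 4.2) has the same Week 12 entries.

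Protocol Section 8.4 describes the visit in prose. Implant parameters are to be assessed before removal, the implant is then removed, and PK timing is explicit: "Blood will be taken for PK pre-explant and 1, 3, 6, 12, 24, 48, 72, 96 hrs after explant". The safety assessments follow in one sentence: "Repeat assessment will be made of adverse effects, vital signs, clinical chemistry, hematology, EKG, concomitant medications, urine drugs, suicidality, depression". The Synopsis end-of-study paragraph reads much the same: "Repeat assessment will be made of adverse effects, EKG, vital signs, clinical chemistry, hematology, concomitant medications, urine drugs, suicidality/depression". Neither list names a physical exam, and neither gives timing for vital signs or EKG.

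**The concern.** The Week 12 visit contains both the last point of drug exposure and a surgical procedure. A value taken before explant describes about 12 weeks on the implant. A value taken after explant also carries whatever the surgery and anesthesia contribute. The two answer different questions, and the Timetable treats them so by asking for vital signs and ECG on both sides of the procedure.

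The prose sections do not carry that distinction, and they omit the exam. Section 8.2 ties its own assessments back to the schedule, "vital signs, adverse events, and clinical chemistries and hematology will be evaluated (per study timetable", but Section 8.4 has no such reference. The Timetable's exam footnote points to Section 8, whose Week 12 text contains no exam. No passage found says which of the two prevails.

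At stake is the end-of-exposure safety reading in the first human study of this implant, with six active subjects planned per dose level. Protocol Section 5.2 names hepatotoxicity and reticulocytes among the things to be followed. Both are laboratory measures, and their Week 12 timing is stated nowhere.

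**Working it through.** No power, alpha or sample-size figure is involved. The check sets the Week 12 entries side by side and counts scheduled readings.

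**Week 12 entries**

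| Item | Protocol and SAP timetables | Section 8.4 | Synopsis | Previous scheduled on-implant value | Last visit in SAP table shell |
|---|---|---|---|---|---|
| Physical exam | Marked | Not listed | Not listed | Week 8 | No table; listing only |
| Vital signs | Before and after explant | Once, untimed | Once, untimed | Week 11 | Table 29: Week 8 |
| 12-lead ECG | Before and after explant | Once, untimed | Once, untimed | Week 8 | Table 30: Week 8 |
| Chemistry | Marked, untimed | Listed, untimed | Listed, untimed | Week 8 | Table 25: Week 8 |
| Hematology | Marked, untimed | Listed, untimed | Listed, untimed | Week 8 | Table 26: Week 8 |

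The Week 11 entry for vital signs comes from the Protocol Timetable and Section 8.3: "Vital signs will be assessed on Days 7 and 10, and on Weeks 2, 3, 4, 5, 6, 7, 8, 9, 10, 11". The Synopsis follow-up paragraph and the SAP timetable still show vital signs at Weeks 4 and 8 only in that period.

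**What one missing pre-explant reading would mean**

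- ECG: on-implant readings at Weeks 4, 8 and 12 pre-explant, so 1 of 3.
- Physical exam: post-dose exams at Weeks 4, 8 and 12, so 1 of 3.
- Chemistry and hematology: 72 hours and Weeks 4, 8 and 12, so 1 of 4 has unstated timing. The value itself is not missing.
- Vital signs: 4 readings from 8 to 72 hours, 2 on Days 7 and 10, and 10 at Weeks 2 to 11. That is 4 + 2 + 10 = 16 before Week 12, or 17 with the pre-explant reading, so 1 of 17.
- Gap to the previous scheduled value: 12 − 8 = 4 weeks for ECG, exam and laboratory tests, which is 4/12 = one third of the implant period. For vital signs it is 12 − 11 = 1 week.

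These are counts of scheduled visits. They do not measure lost information.

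**What the SAP would report**

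The SAP laboratory text promises descriptive statistics at each clinic visit, and its ECG text promises percentages at each timepoint. Both would take in Week 12. The shells for Tables 25, 26, 29 and 30 do not: each ends at Week 8. Other shells do reach Week 12 (Table 21 for the incision site, Tables 22 to 24 for suicidality and depression, Table 28 for urine drugs). The stop at Week 8 therefore looks like an oversight, though the SAP does not say. Nor does the SAP say how two vital-sign or ECG readings from the same visit are to be handled.

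**The case against.** The strongest reply is that the protocol already requires these readings. The Timetable is current text, the SAP repeats it, and Section 8.4 cancels nothing. A narrative that is less detailed than its schedule is an omission, and harm needs a site to disregard the schedule. This stands, and it limits the point to a documentation risk.

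A reader might infer that the last on-drug readings can be taken only after surgery, or lost altogether. The documents do not support that. Vital signs and EKG are named in both prose lists, so only the physical exam could be skipped by someone following the prose. Sentence order does not settle timing either: in Section 8.4 the pre-explant PK sample is mentioned after the removal sentence, so the paragraph is not chronological. The untimed list fits a pre-explant reading as well as a post-explant one.

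A reader might also infer that procedural confounding grows with dose level because more discs are removed. Nothing in the documents quantifies such an effect. Placebo subjects also receive implants and have them removed, so explant effects occur in the comparator too, although the placebo group is small and pooled over one and two implants.

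Three further limits stand. The exam mark sits in a column shared by Weeks 12 and 14, so its exact visit is not fixed. Physical exam findings go only to listings. The removal technique in Appendix B is redacted and the eCRF is not supplied, so timing may be specified where it cannot be seen.

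For chemistry and hematology the Timetable and the prose agree. The issue there is missing timing, not contradiction. The objection does not answer the missing SAP rows.

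**Conclusion.** The mismatch is real and modest. It is an internal inconsistency between the Timetable on one side and Section 8.4 and the Synopsis on the other, not a flaw in the design that the Timetable describes.

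- **Collection.** The risk exists only where staff work from the prose alone. It bears mainly on ECG, physical exam and laboratory tests, where the fallback is Week 8. For vital signs little is lost, provided the weekly schedule in the Timetable and Section 8.3 is the one followed.
- **Reporting.** As the shells stand, Week 12 chemistry, hematology, vital signs and ECG have no summary row even if every reading was taken. The values would still appear in the listings. This part does not depend on how a site reads Section 8.4.

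The conclusion rests on the public text, without Appendix B or the eCRF. It does not extend to a claim that vital signs or ECG go uncollected at Week 12, or that bias rises with dose.

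**What to change.** 1. Reconcile Section 8.4, the Synopsis and the Timetable so that one Week 12 list applies to physical exam, vital signs, ECG, chemistry and hematology, with timing relative to explant stated. Which schedule is right is for the sponsor and the investigator to settle.
2. Identify each Week 12 value as pre- or post-explant, from recorded times or an eCRF field. The PK schedule is anchored to explant, so the explant time should be known. Label any value that cannot be placed as timing unknown.
3. Add Week 12 rows to SAP Tables 25, 26, 29 and 30. Use pre-explant values as the end-of-exposure summary and show post-explant values separately.

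The cost is wording in two protocol sections, one data field or derivation, and a few rows in four table shells. SAP Section 3 says that dose-level 2 data were available before the SAP was finalized, so step 1 may come too late to change collection. Steps 2 and 3 remain useful for the analysis.
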